6.5 Analysis of Safety

Safety analyses will be presented by treatment group and ASP0598 total for SAF, unless specified otherwise.

6.5.1 Adverse Events

AEs will be coded using MedDRA.

For the AEs, the following summaries will be presented:

- An overview of TEAEs and deaths
 - Number of TEAEs
 - Number and percentage of subjects with TEAEs
 - Number of drug-related TEAEs
 - Number and percentage of subjects with drug-related TEAEs
 - Number of serious TEAEs
 - Number and percentage of subjects with serious TEAEs
 - Number of serious drug-related TEAEs
 - Number and percentage of subjects with serious drug-related TEAEs
 - Number of TEAEs leading to treatment discontinuation (MAD and MDE only)

- Number of deaths
- Number and percentage of subjects with TEAEs by SOC and PT for the following:
 - 1) TEAEs
 - 2) Drug-related TEAEs
 - 3) TEAEs Leading to Treatment Discontinuation (MAD and MDE)
 - 4) Serious TEAEs and including number of events
 - 5) Drug-related serious TEAEs and including number of events
 - 6) Common ($\geq 15\%$ in any treatment group) TEAEs for expansion only
 - 7) TEAEs excluding serious AEs and including number of events and number of threshold events. Here threshold equals 5%. This summary will be created only if at least one serious TEAE is present.
- An overview of TEAEs of interest
 - Number of TEAEs of interest
 - Number and percentage of subjects with TEAEs of interest
 - Number of drug-related TEAEs of interest
 - Number and percentage of subjects with drug-related TEAEs of interest
 - Number of serious TEAEs of interest
 - Number and percentage of subjects with serious TEAEs of interest
 - Number of serious drug-related TEAEs of interest
 - Number and percentage of subjects with serious drug-related TEAEs of interest

The above summary will present results for any TEAEs of interest and each of the TEAEs of interest: Cholesteatoma or neoplasm, Ototoxic symptoms (tinnitus, sensorineural hearing loss, dizziness) and Otitis media or otitis externa.

- Number and percentage of subjects with TEAEs of special interest by SOC and PT for the following:
 - 1) TEAEs of special interest for Cholesteatoma or neoplasm
 - 2) TEAEs of special interest for Ototoxic symptoms (tinnitus, sensorineural hearing loss, dizziness)
 - 3) TEAEs of special interest for Otitis media or otitis externa
 - 4) Serious TEAEs of special interest for Cholesteatoma or neoplasm and including number of events
 - 5) Serious TEAEs of special interest for Ototoxic symptoms (tinnitus, sensorineural hearing loss, dizziness) and including number of events
 - 6) Serious TEAEs of special interest for Otitis media or otitis externa and including number of events

6.5.2 Bone Conduction Hearing at 1, 2, 4 kHz by PTA

Descriptive statistics will be used to summarize the bone conduction hearing at each frequency (1, 2 and 4 kHz) and the mean baseline value, post baseline value and change from

baseline at each specified post baseline analysis visit by treatment group.

A summary will also present the number and percentage of subjects with an increase of ≥ 20 dB from baseline for each frequency and the mean bone conduction hearing at each post baseline analysis visit. This summary will also present results for an increase of ≥ 10 dB from baseline at 2 consecutive frequencies (≥ 10 dB at 1 and 2 kHz or ≥ 10 dB at 2 and 4 kHz) for each post baseline analysis visit.

Analysis visits:

SAD	Baseline, Day 2, Day 3 ^a , Week 1, Week 2, Week 4, Week 8, EOS and Maximum ^b
Single dose expansion	Baseline, Week 2, Week 4, Week 8, Week 12, EOS and Maximum ^b
MAD	Baseline, Week 1, Week 2, Week 3, Week 4, Week 5, Week 8, Week 12, EOS and Maximum ^b
Multiple dose expansion	Baseline, Week 2, Week 4, Week 6, Week 8, Week 12, Week 16, EOS and Maximum ^b

^a Day 3 evaluations will only be performed for cohorts 1, 2 and 3.

^b Maximum during study period.

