Prior to any study-related assessments, the Informed Consent Authorization Form will be signed by the subject at Screening (Visit 1). All subjects will enter into a screening period (Days -28 to -1) and will be evaluated for randomization eligibility after completing screening procedures. Eligible subjects will be randomized on Day 1 (Visit 2).

For a subject with bilateral TMP, once both ears have been identified as meeting all inclusion/exclusion criteria at Randomization on Day 1 (Visit 2), the ear with the worse hearing will be selected as the treated ear, unless a rationale exists to treat the other ear. In the case of equivalent hearing level in both ears, the investigator will decide the treatment side with subject and will document the reason in the source document and the eCRF. In the case that the investigator is unable to decide the appropriate ear to treat, consultation with the sponsor may be required.

Dose Escalation

Approximately 20 subjects for SAD and 16 subjects for MAD will be enrolled in dose escalation part of the study. The initiation and selection of dose concentrations for MAD will be based on at least 3 cohorts of SAD.

For SAD, after randomization on Day 1, subjects will receive ASP0598 Otic Solution or placebo administration into the affected ear. Subjects will return to the investigative site for assessments on Days 2, 3, 8, 15, 29, and 57 [End of Study (EOS)]. Day 3 evaluations will only be performed for cohorts 1, 2 and 3.

For MAD, after randomization on Day 1, subjects will receive ASP0598 Otic Solution or placebo administration into the affected ear and will receive additional treatments into the same ear on Days 15 and 29. Subjects will return to the investigative site for assessments on Days 8, 15, 22, 29, 36, 57, and 85 (EOS).

For SAD and MAD, subjects who terminate early from the study will complete EOS assessments.

For MAD only, Subjects who discontinue treatment will be encouraged to complete all protocol defined study visits through the Day 85 (EOS).

The decision to escalate or stop escalation during SAD will be made by the Dose Escalation Committee (DEC). The DEC will operate as per the approved DEC Charter.

The DEC will decide dose escalation and the initiation and selection of doses for MAD cohorts based on the emerging safety and tolerability data from SAD. The tentative starting

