6 STATISTICAL METHODOLOGY

6.1 General Considerations

Continuous data will be summarized descriptively including the number of subjects (n), mean, standard deviation (SD) and/or standard error, median, minimum and maximum.

Categorical data will be summarized by frequencies and percentages. Percentages by categories will be based on the number of subjects with no missing data, i.e. the percentages for the non-missing categories will add up to 100%.

For SAD and MAD, results will be presented by ASP0598 treatment group in each cohort and placebo group where placebo subjects will be pooled across cohorts.

For single dose expansion and multiple dose expansion, results will be presented by each ASP0598 treatment group and placebo group.

All statistical comparisons between ASP0598 and placebo will be conducted using 2-sided tests at $\alpha = 0.05$ significance level, unless stated otherwise. For dose expansion phase, a hierarchical testing method will be used to control familywise error rate where the highest dose group vs placebo will be tested first. Refer to Section [6.4.2](#) for details.

All data summarization and analyses will be performed using SAS® Version 9.4 or higher on Redhat Enterprise Linux. Specifications for tables, listings, and figures (TLF) formats can be found in the TLF specifications.

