6.5.3 Tinnitus Visual Analog Scale (TVAS)

Descriptive statistics will be used to summarize the treated ear TVAS baseline value, post baseline value and change from baseline at each specified post baseline analysis visit by treatment group. Refer to Section 6.5.2 for the list of analysis visits. Number and percentage of subjects will be used to summarize an increase from baseline for the TVAS at each specified post baseline analysis visit by treatment group.

- An increase in tinnitus in any ear.
- An increase in tinnitus in treated ear.

Analysis visits:

SAD	Day 2 to Week 2, Day 2, Day 3 ^a , Week 1, Week 2, Week 4, Week 8 and Maximum*
Single dose expansion	Day 2 to Week 2, Week 2, Week 4, Week 8, Week 12 and Maximum ^b
MAD	Day 2 to Week 2, Week 1, Week 2, Week 3, Week 4, Week 5, Week 8, Week 12, EOS and Maximum ^b
Multiple dose expansion	Day 2 to Week 2, Week 2, Week 4, Week 6, Week 8, Week 12, Week 16, EOS and Maximum ^b

For Day 2 to Week 2, maximum post baseline value during the analysis window will be used.

^a Day 3 evaluations will only be performed for cohorts 1, 2 and 3.

^b Maximum post baseline value during study period.

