6.6 Pharmacokinetic

Descriptive statistics (n, mean, SD, minimum, median, maximum, coefficient of variation (CV), geometric mean, and geometric CV) will be used to summarize baseline value, post-baseline value, and change from baseline at each post-baseline time point for serum concentrations of ASP0598 by treatment group including placebo using the SAF.

Analysis time points:

SAD: Baseline, Day 1 0.5 hour post dose, Day 1 1 hour post dose and Day 3 (Cohorts 1, 2, and 3.) or Day 2 (Cohorts 4, 5, and 6).

MAD: Baseline, Day 1 0.5 hour post dose, Day 1 1 hour post dose, Week 4 predose, Week 4 0.5 hour post dose, Week 4 1 hour post dose.

Dose expansion: Not Applicable.

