6.9.1.2 Analysis Visit Windows

Table 4 Analysis Visit Windows: Bone Conduction by PTA, TVAS, Microscopic Ear Examination and Vital Signs

Analysis Visit	Target Study Day	Analysis Visit Window (Study Day)			
		SAD	Single dose expansion	MAD	Multiple dose expansion
Baseline ^a	1	≤ 1	≤ 1	≤ 1	≤ 1
Day 2 ^b	2	2	NA	NA	NA
Day 2 ^c	2	2 to 3	NA	NA	NA
Day 3 ^d	3	3 to 4	NA	NA	NA
Week 1	8	5 to 11	NA	2 to 11	NA
Week 2	15	12 to 18	2 to 18	12 to 18	2 to 22
Week 3	22	NA	NA	19 to 25	NA
Week 4	29	19 to 39	19 to 39	26 to 32	23 to 36
Week 5	36	NA	NA	33 to 39	NA
Week 6	43	NA	NA	NA	37 to 50
Week 8	57	≥ 40	40 to 74	40 to 74	51 to 71
Week 12	85	NA	≥ 75	≥ 75	72 to 99
Week 16	113	NA	NA	NA	≥ 100
Minimum ^e		≥ 2	≥ 2	≥ 2	≥ 2
Maximum ^f		≥ 2	≥ 2	≥ 2	≥ 2
EOS ^g		≥ 2	≥ 2	≥ 2	≥ 2

^a Baseline value for the above data is based on the last available non-missing value on or prior to the first dose day (Day 1) of study drug within the visit window.

^b For cohorts 1, 2 and 3.

^c For cohorts 4, 5 and 6.

^d Day 3 evaluations will only be performed for cohorts 1, 2 and 3.

^e Minimum value for the above data is based on the minimum of non-missing post-baseline value within the visit window.

^f Maximum value for the above data is based on the maximum of non-missing post-baseline value within the visit window.

^g EOS value for the above data is based on the last available non-missing post-baseline value within the visit window.

For microscopic ear examination, 1 hour post dose analysis timepoint on dosing days will be assigned same as the nominal timepoint.

To identify the value for the analysis, the following rules will apply excluding baseline, minimum, maximum and EOS:

1. For an analysis visit, if a subject has more than one result with a value included within a window, the value closest to the target study day will be used. In case of ties between values located on different sides of the target study day, the later assessment will be used.

2. For the categorical parameter, if a subject has more than one result included within a window, the assessment closest to the target study day will be used. In case of ties between results located on different sides of the target study day, the later assessment will be used.

Planned time points will be used as analysis time points. Concentrations will be excluded from analysis if the actual time from dosing (actual sample date/time – dose date/time) is outside the time window as specified below.

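### SAD worst-value safety rows rest on one fewer scheduled look in cohort 4 (15 µg/mL) than in cohorts 1-3, which tends to make the top single dose look slightly cleaner

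*SAP*

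**What the plan says.** Protocol 4.1 sets the SAD schedule: "Subjects will return to the investigative site for assessments on Days 2, 3, 8, 15, 29, and 57". It then limits Day 3 to cohorts 1 to 3. The current SAD schedule of assessments (Protocol Table 2) has no Day 3 column and gives Day 2 a window of plus one day. SAP 6.5.2 repeats the limit: "Day 3 evaluations will only be performed for cohorts 1, 2 and 3". SAP 7.1 gives consolidation of visits as the reason.

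The worst-value rows are defined as follows.

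- Bone conduction, SAP 6.5.2: the *Maximum* row is the "Maximum during study period".
- TVAS, SAP 6.5.3: "Maximum post baseline value during study period". In the SAD line the mark on *Maximum* is an asterisk with no matching note. I read it as the same definition, which agrees with Table 4.
- TVAS only, SAP 6.5.3: "For Day 2 to Week 2, maximum post baseline value during the analysis window will be used".
- SAP 6.9.1.2, Table 4: "Maximum value for the above data is based on the maximum of non-missing post-baseline value within the visit window", the window being study day 2 onward. The Day 2 analysis window is study day 2 for cohorts 1 to 3 and study days 2 to 3 for cohorts 4 to 6.

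SAP 6.1 shows active subjects by cohort, while "placebo subjects will be pooled across cohorts". For pharmacokinetics, SAP 6.6 lists the last SAD time point as "Day 3 (Cohorts 1, 2, and 3.) or Day 2 (Cohorts 4, 5, and 6").

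**The concern.** A maximum taken over fewer visits can equal, but never exceed, the maximum the same subject would have had with the extra visit. The cohort with the missing visit is cohort 4, at 15 µg/mL. So when cohorts are read side by side on a worst-value row, the comparison leans towards the highest single dose looking cleaner. In a first-in-human dose comparison that is the less cautious direction. Pooled placebo matches neither schedule.

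Bone conduction and TVAS are primary safety endpoints (Protocol 3.1), and safety results after SAD inform whether to open single dose expansion and at which doses (Protocol 4.1 and 9.10). Nothing in the SAP restricts these rows to visits that all cohorts share, and the Day 3 footnote does not say that *Maximum* rests on unequal numbers of looks.

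**Working it through.** The plan gives no figure to reproduce. The looks come from the documents; the chance of a flag per look does not, so it is assumed and shown over a range.

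**Scheduled looks**

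| Row | Cohorts 1-3 | Cohort 4 |
|---|---|---|
| *Maximum* (bone conduction, TVAS) | Days 2, 3, 8, 15, 29, 57: 6 | Days 2, 8, 15, 29, 57: 5 |
| *Day 2 to Week 2* (TVAS) | Days 2, 3, 8, 15: 4 | Days 2, 8, 15: 3 |

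Each SAD cohort has 4 active and 1 placebo subject. Of the 4 pooled placebo subjects, 3 have the longer schedule and 1 the shorter.

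**Chance that a subject is flagged at least once**

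With the same chance p at each look and independent looks, the chance over k looks is 1 − (1 − p)^k. The gap between k and k − 1 looks is p(1 − p)^(k−1). Gaps below are from unrounded values.

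| p per look | *Maximum*, 6 v 5 looks | Gap (points) | *Day 2 to Week 2*, 4 v 3 looks | Gap (points) |
|---|---|---|---|---|
| 1% | 5.85% v 4.90% | 0.95 | 3.94% v 2.97% | 0.97 |
| 5% | 26.49% v 22.62% | 3.87 | 18.55% v 14.26% | 4.29 |
| 10% | 46.86% v 40.95% | 5.90 | 34.39% v 27.10% | 7.29 |

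Pooled placebo at p = 5%, *Maximum*: (3 × 26.49% + 22.62%) / 4 = 25.52%, against 22.62% for cohort 4.

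**Expected subjects among four**

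At p = 5% the gaps are 4 × 0.0387 = 0.15 and 4 × 0.0429 = 0.17 of a subject. Under this model there is a ceiling for any p:

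- p(1 − p)^5 peaks at p = 1/6: (1/6)(5/6)^5 = 0.067, and 4 × 0.067 = 0.27 of a subject.
- p(1 − p)^3 peaks at p = 1/4: (1/4)(3/4)^3 = 0.105, and 4 × 0.105 = 0.42 of a subject.

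**Correlated looks**

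Days 2 and 3 are consecutive days in the same ear, so independence is generous to the concern. Simulation (1,000,000 draws of six correlated normal values, cut so that 5% exceed the threshold at each look) gives:

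| Assumed correlation | *Maximum* | *Day 2 to Week 2* |
|---|---|---|
| Equal, 0.5 | 18.6% v 16.6% | 14.4% v 11.8% |
| Equal, 0.8 | 12.5% v 11.7% | 10.5% v 9.3% |
| 0.90 per day, decaying | 21.6% v 20.5% | 13.6% v 12.3% |

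With correlation of 0.8, or of 0.90 per day, the gap falls to about 1 point.

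**Same mechanism elsewhere**

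In SAP 6.5.4 the Modified Brighton summary takes the worst grade in an interval. The Days 2 to 18 row again has 4 against 3 looks. The row running from Day 1 post dose to the end of study has 7 against 6, because the Day 1 post-dose grade is added to both.

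**Pharmacokinetics**

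The last SAD sample is nominally Day 3 in cohorts 1 to 3 and Day 2 in cohort 4. Each active column carries one nominal day; pooled placebo mixes three Day 3 samples with one Day 2 sample. SAP Table 5 sets no time window for this sample.

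**The case against.** The strongest reply is that this is small and mostly visible already. Safety is descriptive, with no hypothesis testing (Protocol 9.5). Day 3 is already its own row, and Day 2 and Weeks 1, 2, 4 and 8 are reported separately, so cohorts can be compared visit by visit. Using every observed value in a safety maximum is a reasonable choice. At p = 5% with independent looks, Day 3 is a subject's only flagged look with probability 0.05 × 0.95^5 = 3.9%, so the *Maximum* count in a four-subject active arm is unaffected by Day 3 with probability (1 − 0.0387)^4, about 85%.

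All of that stands and limits the size. It does not dispose of the point: per-visit counts cannot be added up to the number of subjects with any flagged value, because the same subject may be flagged at several visits. A like-for-like worst-value count needs its own derivation.

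Three stronger readings are tempting, and the documents do not support them.

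- A reader might infer that cohort 4 must look safer. The rows differ only when the Day 3 value alone is the worst, so this is a tendency.
- A reader might infer that dose and sampling time are fully confounded in the last pharmacokinetic sample. The plus-one-day window lets a cohort 4 Day 2 visit fall on Day 3, and the 0.5 and 1 hour samples are common to all SAD cohorts.
- A reader might infer that these rows drive the expansion decision. Dose escalation uses blinded safety data through Day 15 (Protocol 4.1.1.2), and the expansion criteria sit in the DMC charter and interim analysis plan, which are not among the documents.

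**Conclusion.** The point holds as a minor, inexpensive improvement. The unequal looks (6 v 5 and 4 v 3) and the direction follow from the documents. The size rests on assumptions: an equal chance per look of 1% to 10% and independent looks give about 1 to 6 points for *Maximum* and 1 to 7 points for *Day 2 to Week 2*. Under that model the gap is below half a subject among four at any per-look chance, and correlation between Days 2 and 3 makes it smaller. An effect that showed only on Day 3 would fall outside this model.

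The issue is descriptive and confined to SAD; the multiple dose and expansion parts each use one schedule. For the last pharmacokinetic sample, dose and nominal sampling day are largely, not fully, confounded.

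**What to change.** - **SAP 6.5.2, 6.5.3 and the two worst-grade rows in 6.5.4:** for the comparison across SAD dose levels, add worst-value rows derived from the visits scheduled in all cohorts (Day 2, Weeks 1, 2, 4 and 8; for the Day 2 to Week 2 and Days 2 to 18 rows, Day 2 and Weeks 1 and 2). The row starting on Day 1 keeps its post-dose grade. Leave the existing all-visit rows beside them. Looks then become 5 v 5 and 3 v 3; at p = 5% both schedules read 22.62% and 14.26%.
- **Footnote:** state that the all-visit rows rest on unequal numbers of looks, and that cohort 4's Day 2 visit may fall on Day 3. The common-visit rows equalise the number of looks, not the exact timing.
- **SAP 6.6:** show the last SAD sample as separate Day 2 and Day 3 rows. This does not remove the confounding of dose with day; it stops pooled placebo from mixing the two nominal days.

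The cost is SAP wording and one extra row per table. A change seen only on Day 3 drops out of the common-visit row, but stays in the all-visit row and, for bone conduction, TVAS and the Brighton grade, in the Day 3 row that the SAP already has.

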6.5.3 Tinnitus Visual Analog Scale (TVAS)

Descriptive statistics will be used to summarize the treated ear TVAS baseline value, post baseline value and change from baseline at each specified post baseline analysis visit by treatment group. Refer to Section 6.5.2 for the list of analysis visits. Number and percentage of subjects will be used to summarize an increase from baseline for the TVAS at each specified post baseline analysis visit by treatment group.

- An increase in tinnitus in any ear.
- An increase in tinnitus in treated ear.

Analysis visits:

SAD	Day 2 to Week 2, Day 2, Day 3 ^a , Week 1, Week 2, Week 4, Week 8 and Maximum*
Single dose expansion	Day 2 to Week 2, Week 2, Week 4, Week 8, Week 12 and Maximum ^b
MAD	Day 2 to Week 2, Week 1, Week 2, Week 3, Week 4, Week 5, Week 8, Week 12, EOS and Maximum ^b
Multiple dose expansion	Day 2 to Week 2, Week 2, Week 4, Week 6, Week 8, Week 12, Week 16, EOS and Maximum ^b

For Day 2 to Week 2, maximum post baseline value during the analysis window will be used.

^a Day 3 evaluations will only be performed for cohorts 1, 2 and 3.

^b Maximum post baseline value during study period.

6.5.4 Microscopic Ear Examination

On Day 1, Week 2 (multiple dose only) and Week 4 (multiple dose only), 1 hour after the treatment, number and percentage of subjects will be used to summarize the following canal reactions of treated ear by treatment group:

- Did the Ear experience an abnormal ear sensation
 - No
 - Yes
 - Burning
 - Stinging
 - Itching
 - Pain
 - Other

Percentages for the subcategories of 'Yes' will be based on number of subjects with abnormal ear sensation=Yes.

- After Day 1, for categorical endpoints status of the middle ear and status of the treated tympanic membrane, number and percentage of subjects will be used to summarize baseline value and post-baseline value at each specified post-baseline analysis visit by treatment group. Other parameters will be listed only.

Status of the treated tympanic membrane (Normal, Abnormal, Abnormal: Myringitis, Abnormal: Hematoma, Abnormal: Other, Not visible)

Status of the middle ear in the treated ear (Normal, Abnormal, Abnormal: Mucosal inflammation with effusion, Abnormal: Mucosal inflammation without effusion, Abnormal: Other, Not visible)

Percentages for the subcategories of 'Abnormal' will be based on number of subjects with abnormal.

Analysis visits:

SAD	Day 2, Day 3*, Week 1, Week 2, Week 4, Week 8 and EOS
Single dose expansion	Week 2, Week 4, Week 8, Week 12 and EOS
MAD	Week 1, Week 2, Week 3, Week 4, Week 5, Week 8, Week 12 and EOS
Multiple dose expansion	Week 2, Week 4, Week 6, Week 8, Week 12, Week 16 and EOS

*Day 3 evaluations will only be performed for cohorts 1, 2 and 3.

Number and percentage of subjects will be used to summarize the local skin reaction at the application site by grade as assessed by Modified Brighton Grading Scheme.

- Day 1 post dose through end of study visit by grade, grade 1 or above, grade 3 or above
- Day 1 post dose by grade, grade 1 or above, grade 3 or above
- Day 2 by grade, grade 1 or above, grade 3 or above (SAD only)
- Day 3 by grade, grade 1 or above, grade 3 or above (SAD cohorts 1, 2 and 3 only)
- 2nd dose: post dose through end of study by grade, grade 1 or above, grade 3 or above (MAD and multiple dose expansion)
- 2nd dose: post dose on the dosing day by grade, grade 1 or above, grade 3 or above (MAD and multiple dose expansion)

- 3rd dose: post dose through end of study by grade, grade 1 or above, grade 3 or above (MAD and multiple dose expansion)
- 3rd dose: post dose on the dosing day by grade, grade 1 or above, grade 3 or above (MAD and multiple dose expansion)
- Days 2 to 18 by grade, grade 1 or above, grade 3 or above
- \geq Days 19 by grade, grade 1 or above, grade 3 or above

When assessing severity, if the event changes in severity (0, 1, 1b, 2, 2b, 3, 3b, 4 and 4b where Grade 4b is the worst grade) during a time interval for a subject, the event with the worst grade will be chosen. If the event is reported multiple times with missing grade(s) and with non-missing grade(s) during an analysis period for a subject, then the subject will be counted for the non-missing worst grade. If the event is reported multiple times with all missing grade(s) for a subject, then the subject will be counted as a missing grade.

Refer to Section [6.9.1](#) for end day of end of study visit definition.

